9.3.4 Safety Analyses

The primary endpoint of this study is safety. Please refer to 9.2.2.

9.3.5 Baseline Descriptive Statistics

See 9.2.1 General Approach.

9.3.6 Exploratory Analyses

Exploratory endpoints are listed in Section 3.0 and analyses are listed in 9.2.1 General Approach.

10 REGULATORY AND OPERATIONAL CONSIDERATIONS

10.1 INFORMED CONSENT PROCESS

10.1.1 Consent/Accent Procedures and Documentation

The principles of informed consent obtained by IRB authorized study team members will be in compliance with all IRB requirements. Informed consent will be completed prior to initiation of any study activities. All participants will receive an IRB approved and current consent form containing the purposes, procedures, benefits, and potential hazards of the study. This information will be reviewed with participant by either the principal or a qualified associate investigator. All prospective participants will be given ample time to read the consent form, and ask questions, before signing.

Individual potential participants are required to sign an informed consent document. The original forms will become part of the permanent medical record and kept on file in the participant's medical record, available for inspection by study monitors, auditors, and regulatory authorities, both federal and institutional. Copies will be provided to participants and a copy will be filed in participant's research records. As per regulatory and IRB requirement, informed consent documentation note will be placed in the individual participant electronic record, Clinical Research Information System (CRIS) documenting consent and process used to obtain consent.

The PI will be responsible to ensure that informed consent is obtained in accordance with the relevant Federal regulations and [NIH Policy 301](#). The informed consent will be obtained by the PI or designated investigators that have taken NIMH informed consent course.

All the relevant research information necessary to make an informed decision will be disclosed to the prospective participants. The IRB approved research team member obtaining informed consent is responsible for assuring all potential participant questions have been appropriately answered and the potential participant comprehends information discussed. The individual obtaining the informed consent will make every effort to minimize any possibility of therapeutic misconception.

Consent for NIH staff will be obtained as detailed above with following additional protections:

Consent from staff members will be obtained by an individual independent of the staff member's team whenever possible. Otherwise, the consent procedure will be independently monitored by

the CC Department of Bioethics Consultation Service in order to minimize the risk of undue pressure on the staff member.

10.1.2 Telephone, Remote, and Electronic Consent

The informed consent document will be provided well in advance as a physical or electronic document to the participant or consent designee as applicable for review prior to consenting. A designated study investigator will carefully explain the procedures and tests involved in this study, and the associated risks, discomfort and benefits. In order to minimize potential coercion, as much time as is needed to review the document will be given, including an opportunity to discuss it with friends, family members and/or other advisors, and to ask questions of any designated study investigator. A signed informed consent document will be obtained prior to any research activities taking place.

Informed consent may take place in person or remotely (e.g., via telephone or other NIH approved remote platforms used in compliance with policy, including NIH HRPP Policy 303) per discretion of the designated study investigator and with the agreement of the participant/consent designee(s). Whether in person or remote, the privacy of the subject will be maintained. Consenting investigators (and participant/consent designee, when in person) will be located in a private area (e.g., clinic consult room). When consent is conducted remotely, the participant/consent designee will be informed of the private nature of the discussion and will be encouraged to relocate to a more private setting if needed. If the consent process is occurring remotely, participants and investigators will view individual copies of the approved consent document on screens at their respective locations; the same screen may be used when both the investigator and the participant are co-located but this is not required.

For telephone consent: When the research team study member is satisfied that the potential participant has been given an opportunity to ask questions and all questions have been satisfactorily answered the potential participant will sign and date the informed consent, with the actual date of consent. The original informed consent document will be sent back to the consenting investigator who will sign and date the consent form with the date the consent was returned. A fully executed copy will be sent to medical records and filed in the participant's medical records; a copy will be filed in the research records and a final copy will be returned via mail for the participant's records. Consent documentation will be entered in CRIS with a progress note to the individual participant medical record.

For electronic consent: The study team will confirm with the subject that they are comfortable using the electronic consenting before proceeding with obtaining consent. If not, other methods will be utilized. When an electronic document with a digital signature is used for the documentation of consent, this study will use the iMedConsent™ platform which is 21 CFR, Part 11 compliant to obtain the required signatures. During the consent process, participants and investigators will view the same approved consent document simultaneously in their respective locations. The identity of the participant will be determined by verifying a government issued identification card via the telehealth platform, prior to obtaining the signature. Electronic signature with a timestamp will be provided by required parties through system prompts. Once the completed consent has been saved, it will post to CRIS within a few minutes. All consents completed in iMedConsent™ will post to both the Documents tab and the Consents tab in CRIS. If the research participant has a FollowMyHealth™ account a copy of the completed consent will be posted to

their account within two business days. The study team will provide the research participant with a printed copy of the signed document.

10.1.3 Consent of Subjects who are, or become, decisionally impaired

Adults unable to give consent are excluded from enrolling in the protocol. Adults presenting with representative with legally authorized representation (LAR) documentation will also be excluded from study participation

10.2 STUDY DISCONTINUATION AND CLOSURE

This study may be temporarily suspended or prematurely terminated if there is sufficient reasonable cause. If the study is prematurely terminated or suspended, the PI will promptly inform study participants, the Institutional Review Board (IRB), and Pfizer to provide the reason(s) for the termination or suspension. Written notification, documenting the reason for study suspension or termination, will be provided by the suspending or terminating party to study participants, Pfizer, NIDCR Division of Intramural Research Data and Safety Monitoring Committee (DSMC), and regulatory authorities. Study participants will be contacted, as applicable, and be informed of changes to study visit schedule.

Circumstances that may warrant termination or suspension include, but are not limited to:

- Determination of unexpected, significant, or unacceptable risk to participants
- Insufficient compliance to protocol requirements
- Data that are not sufficiently complete and/or evaluable

Study may resume once concerns about safety, protocol compliance, and data quality are addressed, and satisfy the Institute DSMC and/or IRB.

10.3 CONFIDENTIALITY AND PRIVACY

Participant confidentiality and privacy is strictly held in trust by the participating investigators, their staff, and the Institute and its designees. This confidentiality is extended to cover testing of biological samples and genetic tests in addition to the clinical information relating to participants. Therefore, the study protocol, documentation, data, and all other information generated will be held in strict confidence. No information concerning the study or the data will be released to any unauthorized third party without prior written approval of the Institute and Pfizer.

All research activities will be conducted in as private a setting as possible.

The study monitor, other authorized representatives of the Institute, representatives of the Institutional Review Board (IRB), and/or regulatory agencies may inspect all documents and records required to be maintained by the investigator, including but not limited to, medical records (office, clinic, or hospital) and pharmacy records for the participants in this study.

The clinical study site will permit access to such records.

The study participant's contact information will be securely stored at each clinical site for internal use during the study. At the end of the study, all records will continue to be kept in a secure location for as long a period as dictated by the reviewing IRB, Institutional policies, or Pfizer requirements.

Study participant research data will not include the participant's contact or identifying information. Rather, individual participants and their research data will be identified by a unique study identification number. The study data entry and study management systems used by clinical sites and by research staff will be secured and password protected. At the end of the study, all study databases will be de-identified and archived at the NIDCR.

To further protect the privacy of study participants, a Certificate of Confidentiality has been issued by the National Institutes of Health (NIH). This certificate protects identifiable research information from forced disclosure. It allows the investigator and others who have access to research records to refuse to disclose identifying information on research participation in any civil, criminal, administrative, legislative, or other proceeding, whether at the federal, state, or local level. By protecting researchers and institutions from being compelled to disclose information that would identify research participants, Certificates of Confidentiality help achieve the research objectives and promote participation in studies by helping assure confidentiality and privacy to participants.

10.4 TELEHEALTH AND TELEMEDICINE

During extreme situations when travel to the NIH CC may not be feasible or advisable (e.g., inclement weather, pandemics), telehealth visits may be utilized to include follow-up and unscheduled visits.

ThinkAndor® will be utilized for the conduct of synchronous telehealth/telemedicine visits between NIH healthcare providers and their patients. The provider will document all clinically relevant information collected during the patient encounter in CRIS, just as they do for an onsite visit, and note in the documentation that the encounter occurred via telehealth/telemedicine. Obtaining remote consent via telehealth is explained in 10.1.2.

10.5 OUTPATIENT/OUTSIDE CLINICAL LABORATORY TESTING

Outpatient/Outside Clinical Laboratory Testing may be performed by local CLIA-certified laboratories for study visits for non-local participants that are unable to have laboratory testing performed at the NIH. Participants will be given a laboratory order by the NIH health team to be used at their local CLIA-certified laboratory. Participants and the CLIA-certified lab will be instructed to have lab results sent to NIH via fax within 7 business days (\pm 7 days) to the research team. Additional outpatient blood or urine tests may be ordered as clinically indicated. Lab work to be obtained at local CLIA-certified lab will follow required protocol visit labs.

BLOOD SPECIMENS FOR RESEARCH ASSAYS WILL NOT BE PERFORMED BY OUTSIDE LABORATORIES. FOR REMOTELY COMPLETED SAFETY LABS NOT COVERED BY THE PATIENT'S INSURANCE, WE WILL COVER THE COST FOR COMMERCIAL LABORATORY TESTING.

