6.1.2 Participant Dosing Considerations

Participants entering the study will have mild to moderate disease activity. Based on the known response to Tofacitinib in RA, animal studies, and cellular assays; we expect a similar rapid response in SS participants.

- Any participants experiencing a flare of glandular or extra-glandular manifestations of Sjögren's syndrome, evaluated by the PI or the medically-responsible investigator will be re-evaluated in two (2) weeks (14 days). Study drug will be continued during the monitoring period. If disease activity continues to worsen, the participant will be withdrawn from the study as per Section 7.

Abbreviated Title: Tofacitinib in Sjögren's syndrome

Version Date: 07/01/2024

- Participants with absolute neutrophil count (ANC) 500 to 1000 cells/mm³, will have study drug dosing interrupted until absolute neutrophil count (ANC) is greater than 1000 within 28 days; at that time study drug dosing will resume at 5 mg, orally, twice daily. Otherwise, participants will be withdrawn per Section 7.
- Participants with hemoglobin less than 8 g/dL or a decrease of more than 2 g/dL from baseline will have study drug dosing interrupted and held until hemoglobin values have at least returned to baseline within 28 days at which time study drug will be reintroduced. Otherwise, participants will be withdrawn per Section 7.
- Study drug may be interrupted at the discretion of the investigator if it is in the best interest of the participant.

Drug Administration

A 35-day supply of study drug or placebo will be dispensed to participants on study days 1, 28, 56, 84, 112,140 visits as well as unscheduled visits, if required with instructions regarding the twice daily dosing regimen and a review of potential side effects. No drug will be dispensed to a female participant of reproductive potential until negative pregnancy test results (serum or urine) have been obtained within 24 hours of on site visit.

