6.2.1 Acquisition and Accountability

Pfizer is providing seventy-count (#70) labelled bottles of 5 mg Tofacitinib and placebo. These bottles will be dispensed monthly to the study participants by pharmacy after protocol mandated visit is completed and all clinical and study parameters meet approval of the PI or AI seeing the participant.

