 - A 35-day supply of study drug or placebo will be dispensed to participants on study day 1 with instructions regarding twice daily dosing regimen and a review of potential side effects. No drug will be dispensed to a female participant of reproductive potential until negative pregnancy test results (serum or urine) have been obtained within 24 hours.

Abbreviated Title: Tofacitinib in Sjögren's syndrome

Version Date: 07/01/2024

- For acute infection(s) requiring antibiotics discovered on Day 1: Any participant found to have an acute infection at baseline visit (Day 1 visit) will have the study drug withheld and their next visit will be scheduled for no more than 30 days later;
- Infections prior to 14 days of Day 1: study medication may be administered
- Between -14 to Day 1: study drug will be delayed up to the upper limit of 45 days from screen date
- If the above stated 14 days puts the patient beyond the limits of protocol mandated pre-screening interval, the participant will be excluded from study participation and then give the opportunity to be re-evaluated and re-enrolled.
- If the infection resolves, study medication will be started. If infection does not resolve within 30 days the participant will be removed from the study
- If a medically significant abnormal lab result (i.e., complete blood count, serum chemistries, pregnancy test, urinalysis and random urine protein/creatinine ratio) occurs at baseline (Day 1 visit), requiring repeat for confirmation, the study drug will be withheld and the next visit will be scheduled no more than 30 days later; if repeat testing reveals resolution of abnormal results, participants will be instructed to begin study medication. If the abnormal lab result does not resolve, participants will be removed from the study. Vascular function studies or research labs will not be repeated.

Study Days 7, 21, 42, 70, 154 (+/- 3 days) Telephone Calls

All participants will receive a telephone call from the study coordinator on study days 7, 21, 42, 70, and 154 (+/- 3 days). These calls will confirm study drug compliance, document any adverse events, and record any new or discontinued concomitant medications. A script with standardized questions will be used to confirm compliance with study drug.

Study Day 14/Visit 3: (on site visit)

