All participants will return to the Clinical Center for study day 14 (+/- 7 days); they will be seen in either an outpatient clinic or Day Hospital. The following procedures will be performed at this visit:

- Adverse event assessment
- Concomitant medication review
- Vital sign measurements
- Presenting symptoms, abbreviated medical history and, physical examination
- Laboratory studies:
 - Complete blood count with differential,
 - Serum chemistry panel (creatinine, glucose, urea nitrogen, total bilirubin, alanine aminotransferase, aspartate aminotransferase, alkaline phosphatase, albumin),
 - Pregnancy test (urine or serum; for females of reproductive potential only),

Abbreviated Title: Tofacitinib in Sjögren's syndrome

Version Date: 07/01/2024

- Urinalysis, random urine protein/creatinine ratio,
- BK virus serum and urine quantitative PCR level

Study Days 28 (Visit 4), 56 (Visit 5), 112(Visit 7), 140 (Visit 8)

(on site visits):

All participants will return to the Clinical Center will be seen at the Dental clinic, Outpatient 9 Clinic, or the 5SWS Day Hospital on study days 28, 56,112,140 (all visits +/- 7 days) for a brief visit. Participants will be asked to bring study medication bottle to confirm study drug compliance as well as re-issued of a new 35 day drug supply. The following procedures will be performed at this visit:

- Adverse event assessment
- Concomitant medication review
- Drug accountability-Returning used drug bottle
- Drug accountability- Dispense 35-day supply of study drug
- Vital sign measurements
- Presenting symptoms, abbreviated medical history and physical examination
- Laboratory studies:
 - Complete blood count with differential,
 - Serum chemistry panel (creatinine, glucose, urea nitrogen, total bilirubin, alanine aminotransferase, aspartate aminotransferase, alkaline phosphatase, albumin),
 - Pregnancy test (urine or serum; for females of reproductive potential only),
 - Urinalysis, random urine protein/creatinine ratio
 - Serum complement components C3 and C4,
 - Quantitative immunoglobulins (IgA, IgG, IgM)
 - BK virus serum and urine quantitative PCR level
 - Inflammatory markers (ESR, CRP)
- Assessment of SS disease activity (ESSDAI, PGA)

Study Day 84/Visit 8 (on site visit):

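### Section 10.5 allows outside laboratories 7 business days to report the CBC that triggers dose holds, so a required hold can wait up to 9 to 11 calendar days from the draw, most clearly at Day 14

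*Combined protocol and SAP*

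**What the plan says.** Section 10.5 covers non-local participants who cannot be tested at NIH. Their outside work follows the required visit labs, so it includes the CBC. On timing it says: "Participants and the CLIA-certified lab will be instructed to have lab results sent to NIH via fax within 7 business days", with ± 7 days in parentheses. It does not say whether the clock starts at the draw or at the result, or what the ± 7 days modifies.

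The dosing rules that depend on the CBC are in two places:
- **Section 6.1.2, neutrophils:** a participant with an ANC of 500 to 1000 "will have study drug dosing interrupted until absolute neutrophil count (ANC) is greater than 1000 within 28 days".
- **Section 6.1.2, hemoglobin:** "Participants with hemoglobin less than 8 g/dL or a decrease of more than 2 g/dL from baseline will have study drug dosing interrupted". Neither hold needs a confirmatory repeat.
- **Section 7.1** lists lymphocytes below 500 and ANC below 500, each confirmed by repeat testing, as grounds for stopping study drug.

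On supply, 35 days of drug are "dispensed to participants on study days 1, 28, 56, 84, 112,140 visits". Section 6.2.1 releases each bottle "after protocol mandated visit is completed and all clinical and study parameters meet approval of the PI or AI seeing the participant". Day 14 has a CBC but is not a dispensing visit. It is planned on site: "All participants will return to the Clinical Center for study day 14".

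**The concern.** A dose hold can start only when the team has the result. With every party complying with Section 10.5, a CBC that calls for a hold may reach the team more than a week after the draw while the participant keeps taking tablets already at home. The bottle-release check in Section 6.2.1 governs the next bottle; it does not stop the current one. At Day 14 there is no next bottle, so that check does not operate.

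What is at stake is the timeliness of a safety rule in a trial whose primary objective is safety. The Day 14 CBC is the first one scheduled after dosing starts. If its result can arrive close to Day 28, it loses most of its value as an early check. No estimand, analysis or sample size is involved.

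**Working it through.** **Inputs.** Reporting limit: 7 business days, ± 7 days (Section 10.5). Dose: one tablet twice daily (6.1.1). Bottle: 70 tablets (6.2.1). Supply per dispensing: 35 days (6.1.2). First dose on Day 1 (schedule of activities). Telephone call at Day 21 ± 3 (8.2.1). ANC below 1000 in 0.07% of RA participants in the first three months (2.4.1). Treated arm: 20 (4.1).

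**1. The plan's own supply figure.** 35 days × 2 tablets = 70, which matches the bottle.

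**2. Business days to calendar days.** Assume the clock starts at the draw, the draw day is day 0, and there are no holidays.

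| Draw day | Calendar days to limit | Doses (× 2) |
|---|---|---|
| Mon, Tue, Wed, Sun | 9 | 18 |
| Sat | 10 | 20 |
| Thu, Fri | 11 | 22 |

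If the draw day counts as business day 1, a weekday draw gives 8 to 10 days. If the clock starts at the result, the limit falls later by the laboratory's running time, which is not given.

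**3. The ± 7 days.** If it moves the deadline, the range runs from 9 − 7 = 2 to 11 − 7 = 4 days at the low end, and from 9 + 7 = 16 to 11 + 7 = 18 days at the high end (32 to 36 doses). If it only echoes the visit window in Section 8.1, it changes nothing.

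**4. Tablets in hand.** Before dosing on day v, with full adherence: 70 − 2 × (v − 1).
- Day 14: 70 − 26 = 44 tablets, or 22 days.
- Ends of the Day 14 window: 58 at Day 7 and 30 at Day 21. Either exceeds 22 doses.
- Day 28: 70 − 54 = 16 tablets, or 8 days. Missed doses leave more. At the 80% compliance floor, 0.80 × 54 = 43.2, so at least 44 tablets were taken and up to 26 remain.

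**5. When a Day 14 result is due.** 14 + 9 = Day 23 to 14 + 11 = Day 25, against the next CBC on Day 28. If the deadline is extended by 7 days, Day 30 to 32, after that CBC is drawn.

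**6. The Day 21 call.** Its window is Day 18 to 24. A nominal Day 21 call precedes the Day 23 to 25 due date of a Day 14 draw. A Day 24 call could follow a Day 23 result, and a Day 7 draw is due by Day 16 to 18, before a nominal call.

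**7. Likelihood.** 20 × 0.0007 = 0.014 expected participants with ANC below 1000 over three months. If 10% to 50% use an outside laboratory (assumption), 0.0014 to 0.007. That period also covers the Day 28, 56 and 84 CBCs, so the Day 14 share is smaller. The protocol gives no rate for the hemoglobin hold.

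**The case against.** The strongest reply is that the protocol already has several layers of protection and that the scenario is unusual.

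- **Telephone calls.** Section 8.2.1 says of the calls: "These calls will confirm study drug compliance, document any adverse events, and record any new or discontinued concomitant medications". A reader might infer that laboratory results play no part in them. Section 8.2.5 does not support that: it can be read as making laboratory review part of the adverse event assessment on those calls. This stands as a correction, but a call cannot act on a result that has not arrived.
- **Investigator review.** Section 8.6.4 requires evaluation of all laboratory results, and Section 6.1.2 allows discretionary interruption. Both also wait for the fax.
- **Bottle release.** At an on-time dispensing visit, Section 6.2.1 lets the team hold the next bottle, which limits exposure to what is left at home: about 8 days at Day 28 with full adherence. This stands, but does not reach Day 14.
- **Route and frequency.** Day 14 is planned on site. Section 10.5 is for participants unable to test at NIH, and telehealth under 10.4 is for extreme situations. Section 8.2.11 does allow some outside testing for convenience, but names NIH as the central laboratory. Section 2.4.1 reports that neutropenia was reversible, with no ANC below 500 and no clear link to infection, and minimal hemoglobin effects at this dose. All this stands and keeps the point small.
- **Pregnancy.** A reader might infer that a late outside pregnancy test leaves drug dispensed unchecked. The documents do not support that: no drug goes to a woman of reproductive potential "until negative pregnancy test results (serum or urine) have been obtained within 24 hours of on site visit", and Section 8.8.3 calls for immediate notification.

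None of these supplies a faster route for an outside CBC.

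**Conclusion.** The point holds as a minor patient-safety gap. Section 10.5 applies one slow deadline to all outside visit labs, including the CBC behind the Section 6.1.2 holds and the Section 7.1 stops. The permitted maximum in calendar days rests on three assumptions: the clock starts at the draw, no holidays intervene, and the ± 7 days does not move the deadline.

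Two stronger readings are tempting. One is that holds will start 9 to 11 days later than they would with on-site testing. The documents do not support this: the figure is a limit rather than an expected delay, and the NIH laboratory's turnaround is not stated, so the excess over on-site testing cannot be computed. The other is that a meaningful number of participants would be exposed. The RA rate in Section 2.4.1 implies far less than one neutrophil hold in the treated arm, and the outside route narrows it further. The case for change is that the remedy costs little.

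**What to change.** In Section 10.5, for a CBC with differential done outside NIH:
- Replace the 7-business-day limit with prompt reporting, for example within 1 to 2 business days of the result.
- Require direct notification of the study team for any value meeting a Section 6.1.2 or 7.1 threshold.
- Delete the ± 7 days for these results.
- Print these instructions on the laboratory order.

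Keep the longer limit for results that drive no immediate dosing decision. For scale, 1 business day is 1 calendar day for a Monday to Thursday result and 3 for a Friday result (2 to 6 doses); 2 business days is 2 to 4 calendar days (4 to 8 doses). The laboratory's running time comes on top. The 1 to 2 day limit is a suggestion and has no source in the documents.

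The cost is a wording change and a line on the order form. The downside is that it depends on the outside laboratory's cooperation, so the team must chase late results. Drawing earlier in the window at dispensing visits, or cross-referring to the pregnancy rules, is optional and not needed for this point.
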